#### 13.1.1. Primary Endpoint:

The G-pen acceptance criterion will be based on the sample mean of the treatment minus control failure scores from each subject in the ITT population. If  $D_{ht}$  is the sample mean of the G-Pen minus control failure difference, and SE is the estimated standard error of  $D_{ht}$  (square root of the estimated G-Pen minus control variance divided by the sample size), then the G-Pen will be accepted provided:

$$D_{ht} + 2.6 SE \leq 0.1.$$

This criterion, particularly the value 2.6, came from Monte-Carlo simulations from selected scenarios where the population G-Pen failure rate exceeded the control rate by 0.1. Under these circumstances the rate of G-Pen acceptance was found to be within 0.025 using this criterion, with missing data rates within 15%. This bound of 0.025 on the type 1 error rate was observed for control failure rates up to 5%. Monte Carlo simulation rather than asymptotic normality is necessary because an observed failure from either G-Pen or control is expected to be low, less than 5%.

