The following scoring system will be applied to all subjects in the ITT cohort. If a G-Pen failure is observed then the treatment failure score = 1. Similarly, the failure score = 1 if a control failure is observed. If the treatment outcome is missing, then the treatment failure score = 0.2. A missing control outcome yields a control failure score = 0.1. An observed success for both groups yields

	
a failure score = 0.
 
The G-Pen acceptance criterion will be based on the sample mean of the treatment minus control failure scores from each subject in the ITT population. If <math>D_{ht}</math> is the sample mean and SE is the estimated standard error of the subject treatment minus control failure scores, then the G-Pen will be accepted provided:
 
<math>D_{ht} + 2.6 SE</math> is less than or equal to 0.1.
 
This criterion, particularly the value 2.6, came from Monte-Carlo simulations from selected scenarios, where the population G-Pen failure rate exceeded the control rate by 0.1. Under these circumstances the rate of G-Pen acceptance was found to be within 0.025 using this criterion. The acceptance criterion for the G-Pen in this study will be that the total difference in failures, G-Pen minus Control (i.e., Lilly Comparator), shall not exceed 3 and the total number of failures for the G-Pen shall not exceed 4, after the 75th evaluable subject completes both treatment periods.
 
If the total number of subjects with criterion failures (counted in a blinded fashion) exceeds 4, a monitoring statistician not otherwise involved with study conduct may provide an unblinded determination of the distribution by treatment group for futility only, and communicate a finding of futility (or continue to conclusion) to Xeris' upper management for further decisions, while the study team remains blinded. Success will not be tested and no penalty for this futility only check is planned.

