## **9. STUDY TREATMENTS**

### **9.1. Allocation to Treatment**

Subjects will be randomized to one of the 2 treatment groups to receive the appropriate sequence of blinded study medication (see [Table 3](#)). Approximately 80 patients will be randomized with a goal of completing 75 patients, or roughly 37-38 patients per group. If there are a large number of subjects who are randomized but fail to receive either study drug, compensatory enrollment will be utilized to achieve at least 75 evaluable subjects. Each subject will receive a single subcutaneous injection on each of the two (2) treatment days, with a period of 7-28 days between doses.

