#### 13.1.2. Sample Size Calculation:

Using the above criterion, a sample size of 75 subjects yields probabilities of G-Pen acceptance of over 90% if the population failure rates of G-Pen and control are equal, and the rate of missing observations is within 15%. These results were obtained using Monte Carlo simulations with G-Pen and control total failure rates up to 5%, and with G-Pen success Control failure, or G-Pen failure Control success within 1%.

The power and type 1 error bounds were obtained from a simulation model using a 3x3 table of outcomes for G-Pen and control. The three outcomes for each were Success, Failure, and Missing. Probabilities were assigned to each of the 9 cells, with the missing outcome being

stochastically independent of the Success, Failure outcome combinations. Also the failure score difference, G-Pen minus control, was assigned to each of the nine cells. To simulate one replicate of the study, 75 independent draws were made from the multinomial distribution determined by the probabilities from the 9 cells, and the sample mean, estimated standard error were computed. The G-pen acceptance criterion was applied and either a 0 (G-pen failed) or 1 (G-pen accepted) was recorded. This was repeated 10,000 times to obtain the estimated probability of G-pen acceptance under the conditions defined by the cell probabilities. The simulations were performed using R version 3.1.2 (2014-10-31).

Approximately 80 subjects will be randomized at approximately 8 clinical sites with a goal of no single center accounting for > 20% of the total randomization.

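### The 0.025 type 1 error bound in Section 13.1.1 does not hold over its stated range: with almost no control-only failures the error is up to 5.0% at n = 75

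*Combined protocol and SAP*

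**What the plan says.** Section 13.1.1 bases the primary decision on the mean paired difference in failure score, G-Pen minus control, and accepts G-Pen if Dht + 2.6 SE ≤ 0.1. The multiplier 2.6 was chosen by simulating selected scenarios in which the true excess failure rate was 0.1. Acceptance there is reported as no more than 0.025 "with missing data rates within 15" percent, and the section adds: "This bound of 0.025 on the type 1 error rate was observed for control failure rates up to 5" percent. Simulation is preferred to a normal approximation because "an observed failure from either G-Pen or control is expected to be low, less than 5" percent.

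The Synopsis gives the same result without the range: "Under these circumstances the rate of G-Pen acceptance was found to be within 0.025 using this criterion".

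Section 13.1.2 describes the model as a 3×3 table (success, failure or missing on each drug) from which "75 independent draws were made from the multinomial distribution determined by the probabilities from the 9 cells", with 10,000 replicates. For the power runs it gives total failure rates up to 5%, "with G-Pen success Control failure, or G-Pen failure Control success within 1" percent. Neither section says what discordance the type 1 error runs used.

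**The concern.** With a handful of expected failures, the rule behaves like a cut-off on a small integer count. Its error rate can then jump when n or one cell probability changes slightly, so a bound found in some scenarios need not hold across a range. The scenario least favourable to the rule is one where hardly any subject fails control alone: such failures add to the variance and widen the SE, and without them the SE is at its smallest for a given excess. That scenario is inside the stated range and close to the plan's own expectations. Failures are expected to be rare, and the power runs keep control-only failures within 1%, whereas independent 5% failure rates would give 0.05 × 0.95 = 4.75%.

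This is the only statement of error control for the primary non-inferiority decision. If it is wrong, readers will take the chance of accepting a product 10 points worse to be at most 1 in 40 when it can be higher.

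**Working it through.** **Inputs.** Margin 0.1, multiplier 2.6 and the SE definition: Section 13.1.1. Scores (failure 1, success 0, missing G-Pen 0.2, missing control 0.1): Section 13.1. n = 75 and the 3×3 multinomial model, with missingness independent of outcome: Section 13.1.2. About 80 randomized: Section 9.1.

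**Assumptions.** The variance divisor is n − 1. Missing rates apply per treatment period and are equal on both drugs unless stated. Complete-data results are exact; the others are simulated, mostly with 1,000,000 replicates per point.

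**1. Reproduce the plan's power.** With 4% failing both drugs and 1% in each discordant cell, n = 75, acceptance is 99.3%, 96.7%, 94.3% and 90.7% at 0%, 5%, 10% and 15% missing. The plan's figure of over 90% reproduces, so the model matches the plan's.

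**2. Complete data, n = 75, no control-only failures.** Subjects who fail both drugs contribute a difference of 0, so only the number *a* of G-Pen-only failures matters. With m = a/75, SE = √(m(1 − m)/74).
- a = 3: 0.0400 + 2.6 × √(0.0400 × 0.9600/74) = 0.0400 + 0.0592 = 0.0992, accepted.
- a = 4: 0.0533 + 2.6 × √(0.0533 × 0.9467/74) = 0.0533 + 0.0679 = 0.1212, rejected.

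Divisor n gives 0.0988 and 0.1208, with the same decisions. With a true excess of 0.10, the type 1 error is P(Binomial(75, 0.10) ≤ 3) = 0.00037 + 0.00308 + 0.01268 + 0.03427 = **5.04%**.

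**3. Dependence on n** (complete data, no control-only failures). At n = 74 only 2 failures are allowed and the error is 1.75%; over n = 70–74 it is 1.75–2.4%. At n = 76, 77, 78, 79 and 80 it is 4.7%, 4.4%, 4.1%, 3.8% and 3.5%.

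**4. Dependence on the control-only rate** (complete data, n = 75). At 0.25%, 0.5%, 1%, 2% and 5% the error is 4.4%, 3.8%, 2.9%, 1.8% and 0.85%. It reaches 2.5% at a control-only rate of about 1.3% (about 0.6% at n = 80).

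**5. Equal missingness on both drugs.** Type 1 error (%) by missing rate:

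| n | Control-only | Fail both | 0% | 1% | 2% | 5% | 10% | 15% |
|---|---|---|---|---|---|---|---|---|
| 75 | 0 | 0 | 5.0 | 3.6 | 3.2 | 2.9 | 3.1 | 3.1 |
| 75 | 0 | 5% | 5.0 | 3.6 | 3.2 | 2.8 | 2.7 | 2.5 |
| 75 | 0.5% | 0 | 3.8 | 3.0 | 2.7 | 2.5 | 2.5 | 2.6 |
| 75 | 1% | 0 | 2.9 | 2.5 | 2.3 | 2.1 | 2.1 | 2.1 |
| 80 | 0 | 0 | 3.5 | 3.6 | 3.6 | 3.2 | 2.9 | 2.9 |
| 80 | 0 | 5% | 3.5 | 3.6 | 3.4 | 3.0 | 2.6 | 2.4 |

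At n = 76–79 with a zero control rate, the figure at 1% missing reaches 4.0% (n = 77).

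**6. Other patterns.**
- Independent failures, n = 75: with a 1% control rate, 3.1% complete, 2.6% at 1% missing and 2.2–2.4% at 2–15% missing. At control rates of 2–5% it is about 1–2%, so the bound is met.
- 15% missing on control only, zero control failures: 5.4% (n = 75) and 6.2% (n = 80).
- 5–15% missing on G-Pen only: 1.2–2.4%, bound met.
- Close to the planned case: 80 in the ITT set, about 5 missing one period (5/80/2 = 3.125% per drug, no subject missing both). The error is 3.4%, 2.7% and 2.2% at control-only rates of 0, 0.5% and 1%.

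**7. Simulation noise.** With the plan's 10,000 replicates, the Monte Carlo SE at 0.025 is √(0.025 × 0.975/10,000) = 0.16 points. Values of 2.5–2.8% could pass as 0.025; values of 3.2–5.0% could not.

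**The case against.** The arithmetic is not in dispute; the case against concerns scope and weight.

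- **The plan reports an observation.** It speaks of selected scenarios and of what was found. Those scenarios may have met 0.025, and Section 13.5 defers detail to a separate SAP that is not in the material reviewed. This stands as far as it goes: nothing here shows that the simulation was misreported. But the text turns the observation into a bound for control rates up to 5%, with no lower limit, and a later document cannot make that range true.
- **The 5.04% is a knife-edge.** It needs 75 subjects, no missing outcomes and virtually no control-only failures. That is right, and the usual excess is 0–1 percentage point. Yet 75 is the simulated size, and "Approximately 80 patients will be randomized with a goal of completing 75 patients". The error also stays above 2.5% at n = 75–80 across most of the missing range when control-only failures are absent.
- **The 1% discordance limit belongs to the power runs.** It cannot hold for the G-Pen-only cell when the excess is 10 points. True, but it can hold for the control-only cell, and the plan does not say what was used.
- **The Synopsis count rule gives protection.** It requires that the difference in failures "shall not exceed 3 and the total number of failures for the G-Pen shall not exceed 4". Applied jointly with the SE rule at n = 75, it cuts the error to 0.7% (complete) and 0.7–1.2% (2–15% missing) when 5% fail both drugs. At 2% failing both, complete data still give 3.1%. At zero control failures it accepts 3 versus 0, and the error stays at 5.04%. The rule is also absent from Section 13.1.1.
- **Missing outcomes on control alone are unlikely** in a blinded crossover. Agreed; the 5.4–6.2% figures are a corner case.

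**Conclusion.** The concern holds. The 0.025 is not a bound over the range given in Section 13.1.1. When control-only failures are near zero, the 13.1.1 criterion accepts a product 10 points worse about 1 time in 20 with 75 complete subjects, and about 1 in 28 to 1 in 40 with 1–15% equal missingness at n = 75, against a stated limit of 1 in 40. The doubling is confined to complete data at n = 75, or to missing outcomes falling only on control.

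To simulation error, the bound is met with at least 1% control-only failures and 1–15% equal missingness, and with independent failures at control rates of 2–5%. With complete data at n = 75 and 1% control-only failures it is not quite met (2.9%).

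These figures are for the 13.1.1 criterion alone, with missingness independent of outcome as in Section 13.1.2. The complete-data result is exact and does not depend on the variance divisor. How heavily to weigh a typical excess of under one point is open to judgement; that the sentence is wrong as written is not.

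**What to change.** Keep 2.6. In Section 13.1.1, and in short form in the Synopsis, replace the bound with wording such as:

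> For an ITT sample of 75–80, type 1 error is within 0.025 (to simulation error) when control-only failures are at least 1% and 1–15% of outcomes are missing equally on both drugs. With no control-only failures it is about 2.4–4.0% at 1–15% equal missingness, up to 5.0% with complete data at n = 75, and up to about 6% if missing outcomes fall only on control.

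Rerun the existing simulation at n = 75 and 80 with a control-only rate of 0 and a missing rate of 0 included, and list the scenarios covered, here or in the SAP. Separately, reconcile the Synopsis count rule with the 13.1.1 criterion, so that it is clear which rule or combination decides.

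The cost is wording and a few added simulation scenarios. The criterion, sample size and power stay as they are (about 91% at n = 75 with 15% missing); the stated type 1 error becomes slightly less favourable.

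If the sponsor prefers to guarantee 0.025, that is a design choice. A multiplier of 3.0 holds it for equal missingness of 0–15% at n = 75–80 (maximum about 2.2%). Power at n = 75 would then have to be restated as about 96%, 94%, 90% and 85% at 0%, 5%, 10% and 15% missing (about 87% at n = 80 with 15% missing), so the claim of over 90% would no longer hold at the upper end of the missing range.

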#### 13.1.2. Sample Size Calculation:

Using the above criterion, a sample size of 75 subjects yields probabilities of G-Pen acceptance of over 90% if the population failure rates of G-Pen and control are equal, and the rate of missing observations is within 15%. These results were obtained using Monte Carlo simulations with G-Pen and control total failure rates up to 5%, and with G-Pen success Control failure, or G-Pen failure Control success within 1%.

The power and type 1 error bounds were obtained from a simulation model using a 3x3 table of outcomes for G-Pen and control. The three outcomes for each were Success, Failure, and Missing. Probabilities were assigned to each of the 9 cells, with the missing outcome being

stochastically independent of the Success, Failure outcome combinations. Also the failure score difference, G-Pen minus control, was assigned to each of the nine cells. To simulate one replicate of the study, 75 independent draws were made from the multinomial distribution determined by the probabilities from the 9 cells, and the sample mean, estimated standard error were computed. The G-pen acceptance criterion was applied and either a 0 (G-pen failed) or 1 (G-pen accepted) was recorded. This was repeated 10,000 times to obtain the estimated probability of G-pen acceptance under the conditions defined by the cell probabilities. The simulations were performed using R version 3.1.2 (2014-10-31).

Approximately 80 subjects will be randomized at approximately 8 clinical sites with a goal of no single center accounting for > 20% of the total randomization.

### **13.2. Pharmacokinetic and Pharmacodynamic Analyses**

The pharmacokinetic endpoints will be derived from the individual plasma glucagon and insulin profiles. The pharmacodynamic endpoints will be derived from the individual glucose profiles.

#### **13.2.1. Pharmacokinetic Secondary Endpoints:**

The data for each of the ethnicities/races and the overall population will be analyzed descriptively with AUC,  $C_{max}$  and  $t_{max}$ . Consistent with the objectives of the study (see Section 5.2) PK data will be analyzed from the first 12 subjects to complete treatment with G-Pen in each of the following major ethnicities and races in the US: non-Hispanic Whites, Hispanics, and African-Americans.

#### **13.2.2. Pharmacodynamic Secondary Endpoints:**

Time for plasma glucose to reach >70.0 mg/dL, AUC,  $C_{max}$  and  $T_{max}$  will be compared between the treatment groups using a mixed model with treatment, period and sequence as terms.

Symptom relief will be analyzed as aggregate scores for the four autonomic, four neuroglycopenic symptoms and 8 total symptoms (see [Appendix 1](#)). The time to the minimal score post baseline will be described and compared between the treatment groups using a mixed model with treatment, period and sequence as terms. Similarly, the time to first reporting of “no” for the global hypoglycemia question will be described and compared between the groups.

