1. Subjects will be given an initial IV bolus push dose of regular insulin:
  - a. Dose will be calculated based on the starting plasma glucose level and the subject’s self-reported glucose correction factor.
  - b. Additional bolus doses of insulin may be given as guided by the investigator’s experience if the trajectory of plasma glucose after 30 minutes is > 60 mg/dL. Late bolus doses (i.e., within 20 minutes of dosing) should be avoided.
2. Subjects will be given an IV infusion of regular insulin. The starting IV infusion rate will be based on a subject’s current use of insulin:
  - a. For subjects on insulin pump, the pump will be discontinued and IV insulin infusion will be started at 1.5x the recorded basal rate.
  - b. For subjects on long-acting injected insulin:
    - i. If the subject took their normal evening or morning dose before the visit, IV insulin infusion will be started at 1x the basal rate.\*
    - ii. If the subject did not take their normal evening or morning dose before the visit, IV insulin infusion will be started at 2x the basal rate.\*
  - c. Guided by experience, the investigator may adjust the IV insulin infusion rate at his discretion if the rate of glucose change after 30 minutes is < 1

mg/dL/min.

\* For injected insulin uses, the basal rate will be calculated by dividing the daily dose by 24 to calculate the amount of insulin on board in units/hour.

Plasma glucose measurements will be taken every 15 minutes while glucose is >80.0 mg/dL and at 5-minute intervals once plasma glucose is ≤ 80.0 mg/dL.

Once the initial plasma glucose measurement < 50.0 mg/dL is achieved, the IV insulin infusion will be stopped. During the 5-minute period after the IV insulin infusion has stopped, the glucose level is expected to continue to decrease by approximately 5 mg/dL due to the delayed effect of insulin. Once the confirmatory plasma glucose reading < 50.0 mg/dL is achieved 5 minutes later, subjects will be administered blinded study drug via the subcutaneous route in the upper arm, leg or abdomen.

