**Table 4: Calculation of Starting IV Insulin Infusion Rate**

Subjects on Insulin Pump	Subjects on Long-Acting Injected Insulin	
1. Discontinue the pump	1. Calculate the basal rate in units / hr. (i.e., cumulative basal dose / 24 hrs.)	
2. Start IV insulin infusion at 1.5x the current basal rate	2. Did the subject take their normal daily dose either the evening before or the morning before the visit?	
	YES	NO
	3. Start IV insulin infusion at 1x the calculated basal rate	3. Start IV insulin infusion at 2x the calculated basal rate

- d. Guided by experience and the subject’s HbA1c value at Screening, the investigator may adjust the starting basal rate at his discretion. As a guideline, increasing the basal rate by 25% should be considered for subjects with an A1c > 8.0%. For example, if the subject’s current basal rate is 0.8 units/hour, it would be increased as follows:  $0.8 \text{ units/hour} \times 1.25 = 1.0 \text{ units/hour}$ .
- e. Guided by experience, the investigator may adjust the IV insulin infusion rate at his discretion if the rate of glucose change after 30 minutes is < 1 mg/dL/min.
- f. Once an initial plasma glucose measurement < 50.0 mg/dL is achieved, the IV insulin infusion will be stopped. Note: The requirement is that the average of the readings

from the 2 YSI leads be < 50.0 mg/dL, but it is not required that both readings be < 50.0 mg/dL.

- i. A first baseline PK blood sample should be collected at the point that plasma glucose first reaches a concentration < 50.0 mg/dL.
- g. After 5 minutes, a confirmatory plasma glucose measurement will be performed.
  - i. If plasma glucose remains < 50.0 mg/dL, randomized study drug will be administered (see Section 9.3.3) after collection of a second baseline PK blood sample.
  - ii. If plasma glucose has risen to  $\geq$  50.0 mg/dL, the IV insulin infusion will be restarted and the sequence repeated until there are two consecutive plasma glucose readings < 50.0 mg/dL on record. Note: Only 2 total baseline PK samples should be collected, even if the IV insulin is restarted. The initial PK sample is collected at the first point that a plasma glucose < 50.0 mg/dL is obtained. The second is collected after the confirmatory reading < 50.0 mg/dL is obtained, even if this is more than 5 minutes separated from the initial PK collection.

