**Table 5: Schedule of Assessments**

Assessment	Visit 1	Visit 2	Visit 3*	Visit 4*
	Screening Day -60 to -3	Treatment 1 Day 0	Treatment 2 Day 7-28	Follow-up Day 10-42
Informed consent	x	—	—	—
Medical History & Demographics	x	—	—	—
Inclusion/exclusion review	x	—	—	—
Concomitant medications	x	x	x	x
Height, weight & physical exam a	x	—	—	x
12 lead ECG	x	—	—	x
Vital signs	x	x b	x b	x
Urine pregnancy test	x	x	x	x
Urine drug screen	x	—	—	—
Hematology	x	(x)	—	x
Clinical chemistry	x	(x)	—	x
HbA1c and C-peptide	x	—	—	—
HIV, HCV and HBV	x	—	—	—
Randomization	—	x	—	—
Overnight fast from midnight	—	x	x	—
Administration of study medication	—	x	x	—
Hypo. symptom questionnaire	—	x	x	—
Injection site discomfort scales	—	x	x	—
Draize scales for erythema/edema	—	x	x	—
Glucagon levels (PK) d	—	x	x	—
Venous blood glucose (PD) e	—	x c	x c	—
Review adverse events (AE)	—	x	x	x

a Excluding breast, pelvic and genitourinary exams. Note: height assessment is not required at Visit 4.

b Temperature, respiration, HR and triplicate BP (after >5 min seated rest) will be performed prior to hypoglycemia induction. HR and single BP will be repeated immediately prior to, and at 30, 60, 120 and 240 minutes post-dosing, with ±5 minutes for all procedures.

c If blood glucose is > 270 mg/dL upon clinic arrival, the visit should be rescheduled.

d Venous blood at -5, 0, 10, 20, 30, 45, 60, 90, 120, 180 and 240 minutes post dose, with ±2 minutes for the collections at -5 and 0 minutes, and ±5 minutes for all other samples

e Via rapid glucose analyzer before and during hypoglycemia induction, and at -5, 0, and every 5 minutes post dose through 90 minutes, with ±2 minutes for all collections

(X) = repeat if more than 30 days have passed since Visit 1.

\*Visit 3 should occur 7-28 days following Visit 2, and Visit 4 should occur 3-14 days following Visit 3.

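### The model for time to >70.0 mg/dL leaves out each visit's pre-dose glucose, which is already measured; adding it would give a modest, nearly free gain in precision

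*Combined protocol and SAP*

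**What the plan says.** Section 13.2.2 gives one analysis for the four glucose endpoints (time to >70.0 mg/dL, AUC, Cmax and Tmax): they "will be compared between the treatment groups using a mixed model with treatment, period and sequence as terms". No section adds a baseline term or defines these endpoints as baseline-corrected. Section 13.5 leaves further detail to an SAP, and no separate SAP text is in the file.

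The covariate is already collected. Table 5, footnote e, schedules glucose at both treatment visits "at -5, 0, and every 5 minutes post dose through 90 minutes, with ±2 minutes for all collections". Section 10.2.1 says, of the period after the first reading below 50.0 mg/dL and the stop of the infusion: "After 5 minutes, a confirmatory plasma glucose measurement will be performed". That reading is the last one before study drug.

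The starting value has an upper limit only. If the confirmatory reading is too high, the sequence is repeated "until there are two consecutive plasma glucose readings < 50.0 mg/dL on record". No lower limit is given. The Synopsis adds that between the two readings "the glucose level is expected to continue to decrease by approximately 5 mg/dL due to the delayed effect of insulin".

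**The concern.** A crossover removes stable differences between subjects. It does not remove a difference between one subject's two visits in the glucose level from which recovery starts. Time to >70.0 mg/dL is the time needed to cover a short distance, so a few mg/dL at the start can matter. From 49.9 mg/dL the rise to 70 is about 20 mg/dL; from 40 mg/dL it is 30 mg/dL.

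The pharmacodynamic comparison is the first secondary objective in Section 5.2, and time to >70.0 mg/dL is a named secondary endpoint in Section 5.3.2. What is at stake is the width of the confidence interval for that comparison.

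**Working it through.** **The plan's own figure.** The only power statement (Section 13.1.2) concerns the primary rule: over 90% with 75 subjects. Simulating the plan's 3x3 outcome table reproduces it: 0.908 in the worst stated case (5% failures, 1% discordant cells, 15% missing) and 0.94 to 1.00 in milder cases. No power, SD or rate of rise is given for the pharmacodynamic endpoints, so only n = 75 carries over.

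**Does the design leave spread in the starting value?** Near the threshold, glucose is read "at 5-minute intervals once plasma glucose is ≤ 80.0 mg/dL". The infusion may be adjusted "if the rate of glucose change after 30 minutes is < 1 mg/dL/min", so take a fall of 1 to 2 mg/dL/min near 50 as an assumption. The first reading below 50 then lies anywhere in a band of 5 x 1 = 5 to 5 x 2 = 10 mg/dL. A uniform band of width w has SD w/√12, which gives 1.4 to 2.9 mg/dL. Variation in the further fall of about 5 mg/dL adds to this.

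**Does it move the endpoint?** Starting at 40 rather than 49.9 mg/dL adds 9.9 mg/dL. At an assumed rise of 2 to 3 mg/dL/min that is 9.9/3 = 3.3 to 9.9/2 = 5.0 minutes, roughly one sampling interval.

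**Precision with and without the covariate.** The crossover was simulated with 75 complete pairs. Within-subject differences in time were regressed on sequence, first without and then with the within-subject difference in pre-dose glucose. For complete pairs, the fit without the covariate is equivalent to treatment, period and sequence with a random subject effect.

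Assumptions not in the documents:
- fall near 50 of 1, or 1 to 2, mg/dL/min;
- SD of the further fall 0, 2 or 3 mg/dL;
- rise 2 or 3 mg/dL/min, with within-subject CV 15% or 30% and between-subject CV 25%;
- lag 5 minutes (SD 1.5);
- starting values independent between visits and held below 50.0;
- true difference 2 minutes.

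Times were rounded up to the 5-minute grid. Six of the 24 scenarios, including both extremes, are shown (ratios from unrounded SEs):

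| Fall | SD of further fall | Rise | CV | Pre-dose SD | r | SE without → with | Ratio | Power |
|---|---|---|---|---|---|---|---|---|
| 1 | 0 | 3 | 30% | 1.44 | -0.138 | 0.617 → 0.615 | 0.998 | 0.881 → 0.881 |
| 1 | 0 | 2 | 15% | 1.44 | -0.242 | 0.513 → 0.501 | 0.977 | 0.963 → 0.968 |
| 1-2 | 0 | 2 | 30% | 2.31 | -0.225 | 0.891 → 0.874 | 0.981 | 0.598 → 0.615 |
| 1 | 3 | 3 | 15% | 3.28 | -0.401 | 0.460 → 0.423 | 0.920 | 0.983 → 0.997 |
| 1-2 | 2 | 2 | 15% | 3.05 | -0.448 | 0.576 → 0.517 | 0.899 | 0.929 → 0.971 |
| 1-2 | 3 | 2 | 15% | 3.75 | -0.525 | 0.611 → 0.522 | 0.856 | 0.878 → 0.958 |

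Here r is the correlation between the difference in time and the difference in pre-dose glucose. Over all 24 scenarios the SE fell by 0.2% to 14%, and power rose by 0 to 8 points. In a separate grid with a within-subject pre-dose SD of 1 mg/dL, the SE ratio was 0.993 to 1.001, which is no gain.

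**Closed-form check.** The SE ratio is about √(1 - r²), times a penalty of about 1.4% at n = 75 for estimating one more coefficient. For r = 0.2, √0.96 = 0.980, so about 0.99. For r = 0.3, √0.91 = 0.954, so about 0.97. For r = 0.5, √0.75 = 0.866, so about 0.88. Ignoring the penalty, r = 0.5 is worth 75/0.75 = 100 subjects. The simulation rows above agree with this formula to within about one percentage point.

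**The case against.** The strongest reply is that the entry rule already narrows the starting value, the documents give no SD from which to claim a gain, and the endpoint carries no power statement or success rule. Treatment, period and sequence form a valid crossover model. Section 13.2.2 may also be only a summary: it does not name the random subject effect, and Section 13.5 points to an SAP that could add the covariate. Much of this stands. The size is unknown and may be nil, and nothing decisive depends on it. But the terms as written omit the covariate, and a reference to a document not in the file does not supply it.

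Three stronger readings are tempting, and the documents do not support them.

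- **A large gain.** With a pre-dose SD of 4 mg/dL, a rise of 1 mg/dL/min and other within-subject SD of 3 minutes, the share of variance removed would be (4/1)²/[(4/1)² + 3²] = 16/25 = 64%. But a start near 45 mg/dL, after the expected further fall, would then take (70 - 45)/1 = 25 minutes on average, with SD √(16 + 9) = 5 minutes. That puts about 16% of subjects past 30 minutes (one SD above the mean), whereas Section 13.1.1 expects failures below 5%. Likewise, comparing starts of 44 and 49 mg/dL (26/21 = 1.24) ignores that expected fall. From 45 mg/dL, a start 5 mg/dL lower adds 30/25 = 1.20, or 20%.
- **A spurious drug effect.** A reader might infer that imbalance in starting glucose could pass for a treatment difference. Sequence is randomized 1:1 (Section 8.3), the unadjusted estimate was essentially unbiased in simulation, and its SE already contains this variation.
- **The same gain for every glucose endpoint.** Only time to >70.0 mg/dL has a computed gain. Little is expected for 90-minute AUC, and none has been quantified for Cmax or Tmax.

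**Conclusion.** The point holds as a missed efficiency in one secondary endpoint. The model for time to >70.0 mg/dL omits a baseline that is measured at both visits and is free to vary below 50.0 mg/dL. Under the stated assumptions the SE of the treatment difference would be about 0.2% to 14% smaller with it, and no smaller if the pre-dose SD is near 1 mg/dL. The direction was the same in all 24 scenarios built on the plan's induction rules. The size rests on assumed rates and SDs that the documents do not give. Only precision is affected: the unadjusted comparison remains valid, and the primary analysis does not change. This is a free improvement of low priority.

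**What to change.** In Section 13.2.2 or the SAP, before unblinding, add two terms to the model for time to >70.0 mg/dL: the visit's confirmatory (time 0) plasma glucose, and the subject's mean of that value over both visits. The mean makes the visit value act within subject, so that within- and between-subject relations are not mixed. Name the last confirmatory reading before dosing as the value to use, because the sequence of readings may be repeated. State the random subject effect at the same time.

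The same terms may be used for AUC, Cmax and Tmax for consistency, without a claim of gain.

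The cost is one or two model terms and as many degrees of freedom (for 75 complete pairs, 73 becomes 72 for the within-subject contrast). No new data are needed. Because the reading precedes dosing, that visit's drug cannot affect it.
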